7.6.2. Withdrawal Procedures

Discontinuation of FCX-007 administration does not mean discontinuation from the study. The study assessments and other procedures for the visit and subsequent visits should be completed as indicated in the Schedule of Events (Table 3), and reason for discontinuation of FCX-007 administration should be documented in the subject's source documents and CRF.

If a subject discontinues prior to commencing the long-term safety follow-up period, every effort must be made to perform the study assessments and procedures specified for Visit 6, End of

Treatment (EOT), within 12 weeks (Section 8.5.2.4). The primary reason for subject's withdrawal should be documented in the subject's source documents and CRF.

Every reasonable effort should be made to ensure that subjects who have received one or more FCX-007 injections of any volume are retained in the long-term safety follow-up period (through 15 years).

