12. A skin biopsy for DIF is required at Screening if: 1) subject did not previously have a skin biopsy for DIF performed and results are not contained in the subject's medical records; or 2) the subject was enrolled in a gene therapy trial for EB and did not have a skin biopsy for DIF performed following participation and results are not contained in the subject's medical records.
13. A skin biopsy for DIF is required if: 1) treated wound shows unusual inflammation (beyond temporary inflammation 1-2 days post-injection) suspected to be related to the IP, based on Investigator's judgement; or 2) a post-treatment COL7 serum antibody assay is newly positive or has a clinically significant increased titer from Screening. An unscheduled earlier visit may occur as needed.
14. A skin biopsy for hematoxylin and eosin (H&E) may be collected if: 1) an area injected with IP shows unusual growth; or 2) a DIF biopsy is being collected post-treatment and the investigator feels that the H&E biopsy will add additional information to the DIF biopsy.
15. Optional skin biopsies for IF and IEM will be collected in a subset of subjects that consent to additional biopsies. Baseline biopsies may be collected at any time prior to FCX-007 Day 1 injections and are not required if previously performed and results are contained in the subject's medical records. Biopsies at later intervals are only to be performed if there is a baseline (or prior) biopsy for same evaluations, and biopsies at Weeks 36/Month 9 (V5) and 48/Month 12 (V6) need only be obtained if the prior biopsy demonstrated COL7 expression (for IF) and/or relevant structural changes (for IEM).
16. Results must be reviewed prior to final eligibility determination on Day 1 (V2), the labs may be performed on day of visit, or within 7 days prior to this visit.
17. Blinded assessment is required at Week 12/Month 3 (V3), Week 22, and Week 24/Month 6 (V4 may be completed within 1 day prior to the visit if this is still within the Week 24 Visit window and does not interfere with the time from the Week 22 assessment).
18. Wound assessment (WA) at Week 22 may be performed via remote video assessment, assessment of adequate and current wound imaging, or during a clinic visit.
19. At Week 24/Month 6 (V4) and Week 36/Month 9 (V5) unclosed treatment wounds may be re-treated and unclosed control wounds may be injected.
20. May be completed within 1 day prior to the visit unless otherwise noted.

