8.3. EFFICACY ASSESSMENTS

8.3.1. Wound Assessments by Unblinded and Blinded Investigators

Screening and Baseline assessments necessary for identification, mapping, selection, and labeling of wounds are to be performed by the PI, or trained, medically qualified Sub-I, who will remain unblinded to wound treatment assignment throughout the study.

The Investigator Assessment of Complete Wound Closure of Target Wounds must be performed by a Blinded Investigator at at Weeks 12, 22, and 24 (Table 3). Blinded assessment is also preferred at Weeks 36 and 48.

At all Long-Term Follow-Up visits, the Investigator Assessment of Complete Wound Closure by remote video assessment is encouraged but optional for **treated** Target Wounds (treatment wound), the wounds originally designated as control should not be assessed. This assessment should occur only if the treated Target Wound was closed at Week 48 (Month 12/Year 1) and should cease at further visits if the treated Target Wound is open at any Long-Term Follow-Up visit.

This assessment is to be completed after removal of subject's dressings from target wound pairs (treatment and control wounds) **and prior to any potential disruption of the target wounds** (i.e., surgical pen markings, target wound tracing, bacterial culture of wounds if applicable, FCX-007 administration preparation or administration, or collection of biopsies).

The Blinded Investigator will not have access to the subject's source documents, CRFs, or electronic data capture (EDC) as information regarding target wound randomization and treatment information is available. The Blinded Investigator's assessments will be maintained as separate source documents and stored in a separate location. Written or verbal communication about treatment assignment or interval changes in wounds between those involved in administering FCX-007 (including study team members, subjects and those accompanying subjects at any visit, or others who have knowledge of the wound treatment assignment) and the Blinded Investigator will be discouraged, and a verbal reminder of this requirement will be stated by the Blinded Investigator at the time of the assessments.

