8.5.3. Long-Term Follow-Up

During the long-term follow-up period, the subject and/or their legal guardian, and/or their healthcare provider will be contacted annually to collect information regarding AEs, health changes and relevant concomitant medications (while all concomitant medication use may be reported, the investigator should make every attempt to provide details of concomitant medications used chronically to treat significant diseases or chronic conditions, or any mutagenic medicinal or known exposure to mutagenic agents). Subjects will be encouraged to complete the visit via a remote video visit to allow for the optional efficacy assessment, the Investigator Assessment of Complete Wound Closure. This assessment should occur only for the treated

Target Wound (treatment wound) and not control Target Wound and if the treated Target Wound was closed at Week 48 (Month 12/Year 1) and should cease for further visits if the treated Target Wound is open at any Long-Term Follow-Up visit.

Collection and analysis of a blood sample to monitor for RCL may be performed yearly for up to 15 years. If all post-treatment RCL assays are negative through one year following subject's final IP administration (Week 60 for those who received last injection of FCX-007 at Week 12, or Year 2 for those who received last injection at Week 24 or 36), collection of the yearly follow-up samples may be discontinued.

Any subjects that require tissue biopsies (RCL, insertional mutagenesis, and/or transgene and vector persistence) please contact the sponsor for current procedures.

8.5.4. **Unscheduled Visit**

An unscheduled visit may occur during the study as necessary based on investigator's judgement. At every unscheduled visit, AEs, health changes, and concomitant medications will be assessed. Additional procedures and assessments may be performed based on investigator's judgment.

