6.1.3 Visit Windowing

Data will be summarized based on nominal visit indications with the exception of data captured at early termination and unscheduled visits; data from early termination and unscheduled visits will be summarized based on mapped visit values. The analysis windows for early termination and unscheduled visits are presented in the following table.

Analysis Windows for Early Termination and Unscheduled Visit Mapping

Scheduled Visit	Protocol Specified Window	Analysis Window
Week 12	Week 11 to 16 (Day 78 to 113)	Week 6 to 18 (Day 43 to 126)
Week 24	Week 23 to 28 (Day 162 to 197)	Week 18 to 30 (Day 127 to 210)
Week 36	Week 35 to 40 (Day 246 to 281)	Week 30 to 42 (Day 211 to 294)
Week 48	Week 47 to 52 (Day 330 to 365)	Week 42 to 54 (Day 295 to 379)

Early termination and unscheduled visits will not be mapped to the Week 22 visit.

Data collected at early termination and unscheduled visits prior to study day 78 will not be analyzed, with the exception of those identified as baseline values. Data from assessments performed after study day 379 will not be included in analyses.

The definition for the study day included in each study window is defined as below:

Study Day prior to Day 1 = Visit Date – Day 1 Date

Study Day on or after Day 1 = Visit Date – Day 1 Date + 1

If an assessment's mapped visit is a visit at which the subject has data from a scheduled visit present, or if no analyses are planned for the assessment at the mapped visit, the data collected at the early termination or unscheduled visit will be presented in listings only.

In the event of multiple values from unscheduled or early termination assessments within an analysis window, the value closest to the scheduled visit target study day will be used for analyses. If two values tie as closest to the time point (for example, one value is before and the other value is after the time point), then the later value will be selected.

Data collected at all visits will be included in the data listings with visit presented as reported by the site.

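### SAP 6.1.3 lets closure readings from early-termination and unscheduled visits fill Week 12 or Week 24 without requiring that a Blinded Investigator made them

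*SAP*

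**What the plan says.** **Mapping.** SAP 6.1.3 states that "data from early termination and unscheduled visits will be summarized based on mapped visit values". The analysis window for Week 12 is "Week 6 to 18 (Day 43 to 126") and for Week 24 "Week 18 to 30 (Day 127 to 210"). The text below the table adds that "Data collected at early termination and unscheduled visits prior to study day 78 will not be analyzed", baseline values excepted, so the usable Week 12 window starts at Day 78. Scheduled data take precedence, and nothing is mapped to Week 22. No condition concerns the assessor.

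**Blinding.** Note 17 to the Schedule of Events (Protocol Table 3) reads "Blinded assessment is required at Week 12/Month 3 (V3), Week 22, and Week 24/Month 6". Protocol 8.3.1 and SAP 4.1.3 agree, and call blinding at Weeks 36 and 48 preferred. The PI or Sub-I who selects and labels the wounds is someone "who will remain unblinded to wound treatment assignment throughout the study" (Protocol 8.3.1). The PI or a physician Sub-I also gives the injections (Protocol Appendix 3).

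**The visits that are mapped.** For a subject who discontinues, Protocol 7.6.2 says "every effort must be made to perform the study assessments and procedures specified for Visit 6", within 12 weeks. For unscheduled visits, Protocol 8.5.4 says "Additional procedures and assessments may be performed based on investigator's judgment".

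**Missing data.** SAP 6.1.5 names LOCF as the primary method for the primary and secondary endpoints. SAP 6.7.5 counts missing Week 24 wound assessments as failures in a sensitivity analysis.

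**The concern.** The trial is open-label, the control wound is not injected, and closure is an investigator's visual judgment. The blinded assessor is therefore the main protection of the closure endpoints, and the sponsor made that assessor mandatory at exactly the time points that feed the primary and secondary endpoints. The mapping rule lets a reading without that protection carry the same label. It acts on subjects who leave early or miss the scheduled reading, where knowing which wound was injected could colour the judgment. Because the analysis is now descriptive (SAP 8), the closure percentages are the result itself.

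**Working it through.** **1. The plan's own windows.** The target day is 7 × week + 1, and the visit window in Protocol Table 3 is -1/+4 weeks.
- Week 12: target 85; 85 - 7 = 78 and 85 + 28 = 113.
- Week 24: target 169; 169 - 7 = 162 and 169 + 28 = 197.

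Both agree with the protocol-window column of the table in SAP 6.1.3.

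**2. Days on which a reading can be mapped.**
- Week 12: 126 - 78 + 1 = 49 days, of which 126 - 113 = 13 lie outside the protocol window.
- Week 24: 210 - 127 + 1 = 84 days, of which (161 - 127 + 1) + (210 - 197) = 35 + 13 = 48 lie outside it.

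**3. Closure is in scope.** SAP 6.1.3 does not exempt it. The only assessment scheduled at Week 22 is wound closure (Protocol Table 3), so barring mapping to Week 22 makes sense only if closure readings are otherwise mapped.

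**4. Week 12.** Target wounds must be open at Day 1 (Protocol 8.3.1.2). No closure assessment is scheduled between Day 1 and Week 12, and the Week 12 endpoint has no confirmatory reading. If the scheduled reading is absent:
- without a mapped reading there is no post-baseline closure reading to carry forward, so no success can be scored;
- with one unblinded reading of closed on Days 78-126, the wound is a secondary-endpoint success.

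If the subject then leaves, Weeks 22 and 24 are both missing. LOCF, read literally, fills both with closed and yields a primary-endpoint success. The SAP 6.7.5 sensitivity analysis would score that wound a failure at Week 24, but no failure rule is specified for Week 12.

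**5. Week 24, scheduled reading absent.** Closure is needed at both Weeks 22 and 24 (SAP 6.7.1).

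| Blinded Week 22 | Mapped unblinded Week 24 | Primary result with mapping | Primary result with Week 24 left to LOCF |
|---|---|---|---|
| Open | Either | Failure | Failure |
| Closed | Closed | Success | Success |
| Closed | Open | Failure | Success |

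In the second row the primary result is the same. The sensitivity analysis probably differs: a mapped reading makes Week 24 non-missing, so the failure rule would not apply. In the third row an unblinded reading overturns the blinded one. That favours FCX-007 if the wound is a control and counts against it if the wound is treated.

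If Week 22 is also missing and LOCF runs in visit order, the Week 12 value fills it, and a mapped closed again adds nothing to the primary result. The SAP does not state the carry order. For an in-window Week 24 visit, the earliest permitted Week 22 assessment is Day 162 - 21 = Day 141. A reading on Days 127-140 can therefore be labelled Week 24 before any such Week 22 assessment, and date-ordered LOCF could treat it differently.

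**6. Size per reading.** SAP 7 gives 6 enrolled subjects. One First Pair wound is 1/6 = 16.7 percentage points of an arm's closure rate (1/24 = 4.2 points at the original sample size). The number of early-termination or unscheduled closure readings is not given and cannot be derived.

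**The case against.** The strongest case on the other side concerns the primary endpoint. A reader might infer that an unblinded closed mapped to Week 24 manufactures a confirmed closure. The documents do not support that: Week 22 must be blinded and cannot be filled by mapping, and where it was read closed, LOCF gives the same primary result without the mapped reading. This objection stands. What it leaves is the Week 12 route, the sensitivity analysis and the mapped open.

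Other limits also stand:
- Scheduled data take precedence, so a subject with an extra visit who also has the scheduled reading is unaffected.
- A blinded reader is allowed at these visits and preferred at Visit 6. The plan fails to require one; it does not assign an unblinded one.
- Closure is not a required item at an unscheduled visit.
- Listings show each visit as the site reported it, so a substitution can be traced.

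A reading inside the protocol window is arguably already covered by the requirement for blinding at Weeks 12 and 24. Even so, 13 of the 49 usable Week 12 days and 48 of the 84 Week 24 days lie outside those windows. These counts show where the gap remains; they do not measure bias.

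A reader might also infer an inflated type I error rate. None is involved, because SAP 6.1 plans no statistical testing. Finally, 16.7 points is the weight of any single First Pair wound with 6 subjects, so it shows what one affected reading can do, not what will happen.

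**Conclusion.** The concern holds in a limited form. SAP 6.1.3 can place a closure reading with no blinding requirement in the Week 12 or Week 24 slot when the scheduled reading is absent. The clearest consequence is at Week 12, with a possible carry into the primary endpoint through LOCF. At Week 24 after a blinded closed, a mapped closed affects probably only the sensitivity analysis, while a mapped open changes the primary result.

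Each affected First Pair wound moves a descriptive closure rate by 16.7 points; the total effect cannot be stated. The conclusion assumes that closure falls under the mapping rule, that LOCF is applied as literally written, and that a mapped reading counts as non-missing. The change should be made because the rule can admit biased readings and is cheap to correct, but nothing in the documents shows that any such reading occurred.

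**What to change.** - **SAP 6.1.3:** map a complete-closure reading from an early-termination or unscheduled visit to Week 12 or Week 24 only if the Blinded Investigator made it. Otherwise list it only and do not use it as a source for LOCF.
- **SAP 6.7.5:** count a visit whose only closure reading was excluded in this way as missing, and hence as a failure at Week 24. Also report closure with those readings included.
- **Protocol 8.5.2.4:** ask the already appointed Blinded Investigator to make the closure reading at any early-termination visit up to the end of the Week 24 analysis window (Day 210), by video or same-day image as Protocol 8.5.2.3 already allows at Week 22.
- While editing SAP 6.1.3, reconcile the table's Day 43 start for Week 12 with the text's Day 78 cut-off.

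The cost is a few sentences and no new staff. The downside is that an occasional observed unblinded reading, including an open one, is replaced by LOCF in the primary analysis. That is why the summary with those readings included should be shown beside it.

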8.4.4.2. Hematology and Chemistry

A blood sample for hematology and chemistry analysis will be collected at the time points indicated in the Schedule of Events Table 3. Results from labs collected on Day 1 (Visit 2) must be available and reviewed prior to subject's final eligibility review on Day 1 (Visit 2).

A list of the hematology and chemistry tests and parameters to be analyzed is provided in Table 4.

Hematology and chemistry laboratory analyses will be performed at the investigative site's local laboratory. In the event the local laboratory does not perform selected analyses (i.e. direct or indirect bilirubin, anion gap calculation, globulin, RBC indices, or WBC differential for any lineage or by % or abs counts), these will be considered as not required and are recorded as not applicable for that investigative site.

Table 4: Hematology and Chemistry Analysis

Serum Chemistry/Metabolic Panel		

 • Albumin • Alkaline Phosphatase Total • Anion Gap • ALT (SGPT) • AST (SGOT) • Urea Nitrogen 	
 • Bilirubin, direct & indirect • Calcium • Carbon dioxide • Chloride • Creatinine • Globulin 	
 • Glucose (fasting not required) • Potassium • Sodium • Total Bilirubin • Total Protein
Hematology/Complete Blood Count with Differential		

 • WBC • RBC • Hemoglobin • Hematocrit • Platelet count 	RBC Indices: 
 • MCV • MCH • MCHC • RDW 	WBC Differential: 
 • Neutrophils, % and abs • Lymphocytes, % and abs • Monocytes, % and abs • Eosinophils, % and abs • Basophils, % and abs

abs = absolute; ALT/SGPT = alanine aminotransferase; AST/SGOT = aspartate aminotransferase; MCH = mean corpuscular hemoglobin; MCHC = mean corpuscular hemoglobin concentration; MCV = mean corpuscular volume; RBC = red blood cell(s); RDW = red cell distribution width; WBC = white blood cell(s).

Any clinically significant laboratory results, based upon the opinion of the Investigator, identified from the Screening visit labs will be recorded as medical history and should be evaluated against study exclusion criteria (refer to Section 7.2 for additional details).

Abnormal laboratory values which are unexpected or not explained by the subject's clinical condition should be repeated until confirmed, explained or resolved.

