6.8.3 Clinical Laboratory Evaluation

Local laboratory tests include bacterial wound cultures, urine pregnancy tests, HIV, Hep B, and Hep C, as well as hematology and chemistry. Outside laboratory testing includes genetic testing, RCL analysis and COL7 antibody assays.

Bacterial wound cultures, urine pregnancy tests, HIV, Hep B, Hep C, and genetic testing results will be presented in listings. Hematology and chemistry results will be summarized by visit, presented in listings and presented as shift tables. RCL analysis and COL7 antibody assays will be summarized by visit and presented in listings.

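### The SAP visit-window rule is not limited to efficacy, so safety results from unscheduled and early-termination visits before Day 78 stay out of the by-visit and shift tables, and no worst-value summary picks them up

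*SAP*

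**What the plan says.** SAP 6.1.3 (Visit Windowing) summarizes scheduled data by nominal visit and maps early-termination and unscheduled data to visits through a table of windows. Two rules then restrict the mapped data.

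- Early data: "Data collected at early termination and unscheduled visits prior to study day 78 will not be analyzed", apart from baseline values.
- Later data: if the "mapped visit is a visit at which the subject has data from a scheduled visit present", then "the data collected at the early termination or unscheduled visit will be presented in listings only".

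The section closes by keeping everything visible at subject level: "Data collected at all visits will be included in the data listings with visit presented as reported by the site".

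For the laboratory displays, SAP 6.8.3 says "Hematology and chemistry results will be summarized by visit, presented in listings and presented as shift tables". RCL and COL7-antibody results get by-visit summaries and listings. SAP 6.8.4.1 presents vital signs by visit. None of these sections defines a worst post-injection value or an any-time post-injection result.

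The protocol provides for samples outside the schedule. Under Protocol 8.4.4.2, unexpected or unexplained abnormal values "should be repeated until confirmed, explained or resolved". Protocol 8.5.4 allows further procedures at an unscheduled visit at the investigator's discretion. Protocol 7.6.2 asks for the Visit 6 assessments when a subject leaves early.

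**The concern.** Nothing in SAP 6.1.3 confines the exclusions to efficacy, and its place under General Methodology suggests that they apply throughout. After Day 1, Protocol Table 3 schedules hematology, chemistry, vital signs, RCL and COL7 antibody only at Weeks 12, 24, 36 and 48. Apart from a Week 12 visit held ahead of its window, every post-injection result in the first 11 weeks must come from an unscheduled or early-termination visit, which is the kind of data that the rule sets aside.

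Suppose a laboratory value is abnormal at an unscheduled visit after the first injection and normal again at Week 12. The shift table would show that subject as normal at baseline and normal afterwards. The efficacy analysis is now descriptive (SAP 8), so the safety tables are a main output of the study and should reflect all post-injection results that were collected.

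**Working it through.** **1. Reproduce the windows in SAP 6.1.3.** The SAP counts Day 1 as the first day, so Week w falls on Day 7w + 1. The Table 3 window is -1/+4 weeks.

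- Week 12: 7 × 11 + 1 = Day 78 to 7 × 16 + 1 = Day 113, as stated.
- Weeks 24, 36 and 48: Days 162–197, 246–281 and 330–365, as stated.
- Analysis windows run from 7 × (lower week) + 1 to 7 × (upper week): 43–126, 127–210 and 211–294, as stated. The last gives 295–378 against a stated 379. That one-day difference does not affect this point.

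**2. Period with no scheduled safety sample.** Day 1 is dosing and the Week 12 window opens on Day 78. Days 2 to 77 are 77 − 2 + 1 = 76 days. They make up 76/378 = 20.1% of the post-injection days to Day 379 (379 − 2 + 1 = 378).

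**3. Which rule applies when** (unscheduled and early-termination results):

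| Study day | By-visit and shift tables | Listings |
|---|---|---|
| 2–77 | Out | In |
| 78–379, mapped visit has scheduled data | Out | In |
| 78–379, scheduled data absent | Can enter | In |

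SAP 6.8.3 does not say which post-baseline value feeds the shift tables. The table above takes the words of 6.1.3 at face value for them.

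**4. Internal conflict.** The Week 12 analysis window has 126 − 43 + 1 = 84 days. Of these, Days 43 to 77 (77 − 43 + 1 = 35 days, 42%) are assigned to Week 12 by the table and then excluded by the text.

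**5. Share of unscheduled results left out of the tables.** The documents give neither the number of unscheduled results nor the completeness of scheduled visits. *Assume* that unscheduled results are spread evenly over Days 2 to 379 and that the scheduled value is present with probability c. The share left out is then at least 1 − (302/378) × (1 − c), where 302 = 378 − 76.

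| c | Share left out (at least) |
|---|---|
| 70% | 76% |
| 80% | 84% |
| 90% | 92% |
| 95% | 96% |
| 100% | 100% |

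These are shares of an unknown and possibly very small count. The share left out of the listings is 0%.

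**6. Early leavers.** Protocol 7.6.2 allows 12 weeks (84 days) for the Visit 6 assessments. A subject leaving on Day 40 could be seen as late as Day 40 + 84 = Day 124, which maps to Week 12 and can be tabulated. If the visit falls before Day 78, its laboratory, RCL and antibody results are collected but left out of the summaries. With 6 enrolled subjects (SAP 7), one such subject would be 1/6 = 17%.

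**The case against.** A reader might infer that toxicity between visits is reported as absent. The documents do not support that, for four reasons.

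- All results are listed, and with 6 enrolled subjects the listings can be read in full.
- TEAEs are defined by onset date (SAP 6.8.2), with no visit window. AEs are collected at every unscheduled visit and at phone contacts 3 days after injection and at Week 6. A clinically significant laboratory change can be recorded as an AE (Protocol 8.4.5.1).
- A positive RCL qPCR result has its own path under Protocol 7.6.1: administration is suspended and the result is shared with investigators, the DSMB and regulators.
- A by-visit table describes status at the visit. It makes no claim about the time between visits.

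A reader might also infer that the rule removes the results most likely to show harm. That goes too far. A repeat draw follows an abnormal value, and if that value was first found at a scheduled visit it is tabulated. The earlier visit mentioned in Protocol 8.4.4.7 is for a skin biopsy, not for further antibody or RCL blood samples. Nor does everyone who stops early lose all post-baseline values. Stopping injections is not leaving the study, and an early leaver's assessments may fall on or after Day 78.

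These points limit the consequence but do not answer the core of it. The AE route depends on the investigator's judgment, and Protocol 8.4.5.1 does not count abnormal findings associated with the underlying disease as AEs unless they are more severe than expected. It cannot replace a laboratory summary. The words of SAP 6.1.3 do not exempt AE data by name either, although 6.8.2 plainly intends AEs to be counted by onset.

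**Conclusion.** The point holds in a limited form. SAP 6.1.3 as written keeps collected post-injection safety results out of the summary tables. This covers all unscheduled and early-termination results on Days 2 to 77, and later ones whenever the mapped visit has scheduled data. SAP 6.8.3 has nothing to compensate. An abnormality found only at such a visit on Days 2 to 77 is missing from the by-visit and shift tables. It is still listed, and it is tabulated as a TEAE if the investigator records it as one.

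The size in practice cannot be given, because there is no stated rate of unscheduled sampling. The 76–100% range above rests on an assumed even spread and on 70–100% completeness of scheduled visits. The Day 43 against Day 78 conflict (35 of 84 days) needs no assumption and should be corrected in any case.

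This is an inexpensive improvement to the safety summaries. It is not evidence that harm would go unreported.

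**What to change.** 1. **SAP 6.1.3, scope.** State that the mapping and exclusions govern by-visit summaries only, and that they do not apply to AE data. Keep the scheduled value where one exists. Without that sentence there would be no rule for choosing between a scheduled and an unscheduled result, because the closest-value rule covers only several unscheduled or early-termination values.
2. **SAP 6.1.3, windows.** Reconcile the Day 43 start of the Week 12 analysis window with the Day 78 exclusion, by moving one or removing the other.
3. **SAP 6.8.3.** Keep the by-visit tables. Add a shift table from baseline to the worst post-injection value, drawn from scheduled, unscheduled and early-termination results. Add a row for any post-injection result to the RCL and COL7-antibody summaries.

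The cost is a few sentences of SAP text and one derived record per parameter. The tables will look slightly less favourable, because repeat draws tend to follow abnormal values. A footnote can say so.
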